#### **6.5. Concomitant Therapy**

At each study visit, the site personnel should question the participant regarding any medications taken and vaccinations received by the participant and record the information as specified in [Section 6.5.1](#).

##### **6.5.1. Recording of Concomitant Medications and Non-study Vaccinations**

The following concomitant medication(s) and vaccine(s) must be recorded in the eCRF:

- All non-study vaccinations administered during the period starting  $\leq 28$  days before the first dose of study vaccine.
- COVID-19 vaccination (regardless of type of vaccine) will be recorded anytime from Day 1 through the End of the Study (Day 504)
- All concomitant medications and non-study vaccinations taken through 28 days after each vaccination. Antipyretics and analgesics taken prophylactically (ie, taken in the absence of any symptoms in anticipation of a vaccination reaction) will be recorded as such.
- Any concomitant medications relevant to or for the treatment of an SAE or a MAAE.

- Prophylactic medications (ie, medication administered in the absence of any symptom and in anticipation of a reaction to the vaccination) from Day 1 through 28 days after each dose. For example, an antipyretic or analgesic is considered to be prophylactic when it is given in the absence of fever and any other symptom, to prevent fever from occurring.
- Participant will be asked if they have taken any antipyretic or analgesic to treat or prevent fever or pain in the electronic diary (eDiary) within 7 days post vaccination, including day of vaccination. Reported antipyretic or analgesic medications should be recorded in the source document by the site staff during the post vaccination study visits or via other participant interactions (eg, phone calls).

#### **6.5.2. Concomitant Medications and Non-study Vaccinations that May Lead to the Elimination of a Participant from Per-Protocol Analyses**

The use of the following concomitant medications and non-study vaccinations will not require withdrawal of the participant from the study but may determine a participant's inclusion in Per-protocol (PP) analyses. Analysis sets are described in [Section 9.4](#).

- Any investigational or nonregistered product (drug or vaccine) other than the study vaccine used during the study period.
- Immunosuppressants or other immune-modifying drugs taken or administered chronically (ie, more than 14 days in total) during the study period. For corticosteroids, this will mean that prednisone  $\geq 20$  mg/day or the equivalent is not permitted. Inhaled and topical steroids are allowed.
- Long-acting immune-modifying drugs taken or administered at any time during the study period (eg, infliximab).
- A non-study vaccine administered within 28 days prior to or after any study vaccination, except for any licensed influenza vaccine, which can be administered  $>14$  days before or after any study vaccination. COVID-19 vaccines (regardless of manufacturer) may be administered  $> 7$  days but preferably  $> 14$  days before or after any study vaccination, with the intention of prioritizing COVID-19 vaccination over all other considerations.
- Immunoglobulins and/or any blood products administered during the study period.

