-  All scheduled study visits should be completed within the defined visit window. Timing of Dose 3 is calculated in relation to Dose 1 (Day 1) and should not shift later than 167 days ( $\pm 7$  days) after Day 1; succeeding follow-up visits (Visits 10-17) are scheduled in relation to Dose 3. In the event the participant is not able to come on site for a clinic visit as a result of the COVID-19 pandemic (self-quarantine or disruption of clinical site activities following business continuity plans and/or local government mandates for “stay at home” or “shelter in place”), a safety call to the participant should be made in place of the clinic visit. The safety call should encompass all scheduled visit assessments that can be completed remotely, such as assessment for AEs and concomitant medications (eg, as defined in scheduled safety calls at Visits 12-15). Home visits will be permitted for all non-dosing visits in the event a participant cannot make it to the clinic as a result of the COVID-19 pandemic. Home visits must be permitted by the site IRB and the participant via informed consent and have prior approval from the Sponsor (or its designee).

-  In the event the visit for Dose 2 is disrupted and cannot be completed at Day 56  $\pm$  7 days as a result of the COVID-19 pandemic (COVID-19 vaccination under the FDA EUA or FDA approval, self-quarantine or disruption of clinical site activities following business continuity plans and/or local government mandates for “stay at home” or “shelter in place”), the window may be extended to Day 56 + 56 days (i.e., to 4 -months). When the extended window is utilized, the Day 84 visit is to be completed at 28 (-7 to +21) days after Dose 2 and monthly safety calls should occur every 28 days  $\pm$  7 days until the Month 6 visit (Day 168) for Dose 3. Dose 3 timing should continue to be based on Dose 1 and should not be adjusted if Dose 2 occurs in the extended dosing window (Dose 3 should not shift later than 167 days [ $\pm$  7 days] after Day 1); succeeding follow-up visits (Visits 10-17) are scheduled in relation to Dose 3.
-  Only documentation of COVID-19 vaccine is required.
-  Upon completion of final study procedures, including the final assessment and recording of MAAEs and SAEs, the participant’s treatment assignment may be unblinded via the IRT system.

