### **8.9.3. Safety Phone Calls**

A safety phone call is a telephone call made to the participant by trained site personnel. This call will follow a script, which will facilitate the collection of relevant safety information. The participant will be interviewed according to the script, and information relating to MAAEs, SAEs, and concomitant medications associated with these events; receipt of non-study vaccinations and AEs leading to study withdrawal will be collected.

Participants will have 6 safety phone calls on Day 112, Day 140, Day 224, Day 252, Day 280, and Day 308 to collect MAAEs, SAEs, concomitant medications associated with these events, receipt of non-study vaccinations, and AEs leading to withdrawal.

Participants who miss the second vaccination for any reason and are expected to receive the third vaccination will have safety calls at Visit 6 (Month 3), Visit 7 (Month 4), and Visit 8 (Month 5). They should follow the same script as the other safety calls performed during the study.

All scheduled study visits should be completed within the defined visit window. In the event the participant is not able to come on site for a clinic visit as a result of the COVID-19 pandemic (self-quarantine or disruption of clinical site activities following business continuity plans and/or local government mandates for “stay at home” or “shelter in place”), a safety call to the subject should be made in place of the clinic visit. The safety call should encompass all scheduled visit assessments that can be completed remotely, such as assessment for AEs and concomitant medications (eg, as defined in scheduled safety calls at Visits 12-15). Home visits will be permitted for all non-dosing visits in the event a participant cannot make it to the clinic as a result of the COVID-19 pandemic. Home visits must be permitted by the site IRB and the subject via informed consent and have prior approval from the Sponsor (or its designee).

All safety information described by the participant must be written down in a designated location within the source documents and not written on the script used for the telephone call.

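### Several per-protocol exclusions run for the whole study, but the exposures that trigger them must be recorded only for 28 days after each dose or when tied to an SAE or MAAE

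*Protocol*

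**What the plan says.** Protocol Section 6.5.2 lists exposures that "may determine a participant's inclusion in Per-protocol (PP) analyses". Four of them run over the whole study:

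- "Immunoglobulins and/or any blood products administered during the study period"
- "Long-acting immune-modifying drugs taken or administered at any time during the study period"
- immune-modifying drugs "taken or administered chronically (ie, more than 14 days in total) during the study period"
- any other investigational or unregistered product

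A fifth concerns timing around doses: "A non-study vaccine administered within 28 days prior to or after any study vaccination", with shorter intervals for influenza and COVID-19 vaccines.

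Section 6.5.1 sets what must be entered in the eCRF. The general requirement is "All concomitant medications and non-study vaccinations taken through 28 days after each vaccination". Added to it are non-study vaccines in the 28 days before Dose 1, COVID-19 vaccines from Day 1 to Day 504, and drugs relevant to an SAE or MAAE. Table 1 footnote 11 dates the last item: MAAE-linked drugs to Day 336, SAE-linked drugs to Day 504. Section 6.5 has staff ask about medications and vaccines at every visit, but record them as Section 6.5.1 specifies.

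On the safety calls the protocol says two things. Section 8.9.3 states that "receipt of non-study vaccinations and AEs leading to study withdrawal will be collected", and Table 1 footnote 10 agrees. Footnote 15 is attached to the medication and vaccination row at those same calls and at Days 336 and 504. It reads "Only documentation of COVID-19 vaccine is required".

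The PP Set is the primary immunogenicity population (Protocol Section 9.4.5; SAP Section 5.5). SAP Section 6.4.2 fits PP-based ANCOVA models to neutralizing titers at Months 3, 7, 12 and 18.

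**The concern.** An exclusion rule can act only on what reaches the database. Here the rule and the recording have different time spans. Immunoglobulin or plasma can bring in donor antibody and raise a titer; immunosuppressants can lower it. The net direction of any error is therefore unknown.

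Uniformity is also at stake. Take two participants with the same drug exposure on the same day. One received it for an adverse event that led to a healthcare visit, so it is recorded and judged. The other received it at a planned visit for an existing condition that had not worsened, so nothing need be recorded. The cumulative 14-day count is the most exposed rule, because it cannot be totalled across unrecorded gaps.

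SAP Section 6.2.6 leaves the major-deviation rules to be settled before database lock. Rules written then cannot use data that sites were never required to enter. The Month 12 and Month 18 results would carry the per-protocol label with only partial screening.

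**Working it through.** The documents state no coverage figure, so there is none to reproduce. The check is a count of days.

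**Inputs.** Doses on Days 1, 56 and 168 (Protocol Section 4.1.2). Last visit Day 504 (Table 1). A 28-day period is the dose day plus 27 days (Synopsis, safety assessments; SAP Appendix C). Antibody draws on Days 29, 56, 84, 168, 196, 336 and 504 after baseline (Section 8.8).

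**General recording, three doses.** Windows are Days 1-28, 56-83 and 168-195, so 3 × 28 = 84 days and 84/504 = 16.7%. Counting one further day per window gives 87/504 = 17.3%. The gaps are Days 29-55 (27 days), 84-167 (84 days) and 196-504 (309 days): 27 + 84 + 309 = 420 = 504 − 84.

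**Continuous reading.** SAP Section 6.2.4 summarizes medications over one period from the first dose to 28 days after the last. Applied to recording, that is Days 1-195, or 195/504 = 38.7%.

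**Fewer doses.** Two doses (Table 6, to Day 420): 56/420 = 13.3%. One dose (Table 7, to Day 336): 28/336 = 8.3%.

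**Coverage before each draw** = recorded days before draw day *t*, divided by *t* − 1:

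| Draw | Three separate windows | Continuous to Day 195 |
|---|---|---|
| Day 29 | 28/28 = 100% | 100% |
| Day 56 | 28/55 = 50.9% | 100% |
| Day 84 | 56/83 = 67.5% | 100% |
| Day 168 | 56/167 = 33.5% | 100% |
| Day 196 | 84/195 = 43.1% | 100% |
| Day 336 | 84/335 = 25.1% | 195/335 = 58.2% |
| Day 504 | 84/503 = 16.7% | 195/503 = 38.8% |

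Months 12 and 18 fall short on either reading. The shortfall at Days 56 to 196 depends on the stricter one.

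**Event-linked recording.** MAAE-linked drugs are required on 336/504 = 66.7% of days; SAE-linked drugs and COVID-19 vaccines on all 504. Over Days 337-504 (168 days) the MAAE route has closed. Table 1 schedules no contact between the Day 336 and Day 504 visits, and footnote 15 applies at both.

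**Vaccines other than COVID-19, 28 days before each dose, under Section 6.5.1.** Dose 1: 28/28. Dose 2 (Days 28-55): 1/28, or 2/28 with the extra day. Dose 3 (Days 140-167): 0/28. If Section 8.9.3 governs, the Day 140 call asks about vaccines, but at its nominal date it falls on the first day of the Dose 3 window. No call falls in the Dose 2 window. The Day 56 and Day 168 visits carry the recording row without footnote 15, but under footnote 11, which repeats the post-dose limit.

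**The case against.** The best defence is that these products are prescribed or administered by clinicians. Participants are healthy at entry, and immune-mediated disease is excluded. The MAAE definition in Section 8.9.1.4 is broad and covers unscheduled study-clinic visits. Much new use would therefore arise from a recordable event, and to Day 336 the drug would be recorded with it. This stands. A reader might infer from the 17% that 83% of the study is unscreened, or that an exposure on Day 100 or Day 300 need not be recorded at all. The documents do not support that: both days lie inside the MAAE-linked period. The gap concerns exposures not tied to a MAAE or SAE, and after Day 336 those not tied to an SAE.

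Four other limits also stand:

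- The rule says exposures may determine inclusion; it does not remove participants automatically.
- PP criterion (c) applies to the period of the analysis in question. A late exposure has no bearing on Month 3, and coverage is 100%, 51% and 67% before Days 29, 56 and 84 even on the stricter reading. It would be wrong to say that the rules fail for most of the data, or that the Month 3 dose selection is undermined.
- The vaccine gap does not extend to Dose 1 or to COVID-19 vaccines.
- Section 7.2 has the eCRF document receipt of another investigational product as a reason for withdrawal. That helps only if the participant is withdrawn, which Section 6.5.2 says is not required.

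The SAP's continuous period and its listing of post-period medications soften the count. They describe how data are displayed, however, and require no collection after about Day 195.

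**Conclusion.** The mismatch is real and should be corrected. General recording covers 17% of study days for three-dose participants, or 39% on the most generous reading. Event-linked recording adds to this but does not close the gap. Exposures outside the windows and not linked to a MAAE or SAE cannot be screened fully or uniformly. This matters mainly for the Month 12 and Month 18 PP results, and most for Days 337-504. Separately, footnote 15 contradicts Section 8.9.3 and footnote 10, and vaccines other than COVID-19 before Doses 2 and 3 are not clearly covered.

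The counts assume nominal dose days and the 28-day convention above. The number of participants affected cannot be derived: the documents give neither an exposure rate nor the share caught through MAAE or SAE recording, which could be anything from 0 to 100%. A reader might assume that 1-3% of 452 participants are exposed (5 to 14 people) and treat all of them as wrongly retained. That rate is not in the documents, and event-linked recording would catch some of them.

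**What to change.** In Section 6.5.1, Table 1 footnotes 11 and 15, and the matching footnotes of Table 6 (10 and 14) and Table 7 (10 and 13), require recording of every exposure listed in Section 6.5.2 from Day 1 to the last visit. These are immune-modifying drugs with start and stop dates, immunoglobulins and blood products, investigational products, and all non-study vaccines. Use the calls and visits already scheduled. Reconcile footnote 15 with Section 8.9.3 and footnote 10 so that sites have one instruction for the calls.

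For participants already past those visits, ask at the next contact. SAP Section 7 reports that all Part 1 participants had completed or discontinued by the time the Part 2 seven-month interim analysis was planned, so this will not always be possible. Where it is not, state in the SAP and CSR that the Month 12 and Month 18 PP Sets were screened only for recorded exposures.

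The cost is footnote and eCRF-instruction wording plus one more scripted question at existing contacts, with no new visit. The downside is possibly a few more PP exclusions.

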## **6.6. Intervention After the End of the Study**

Any AE occurring at any time outside the observation period or after the end of the study and considered to be caused by the study vaccine must be reported to the Sponsor.

## **7. DISCONTINUATION OF VACCINATION AND PARTICIPANT DISCONTINUATION/WITHDRAWAL**

### **7.1. Discontinuation of Vaccination**

A “withdrawal” from the study vaccine refers to any participant who does not receive all study vaccinations from the date of withdrawal due to either participant request or Investigator recommendation. A participant who withdraws from further study vaccination but does not withdraw consent will be followed for safety and immunogenicity as outlined in [Appendix 2](#). The Investigator should make all efforts to ensure that the participants remain in the study to ensure a proper safety follow-up. The reason for participant withdrawal from study vaccination must be documented in the appropriate source documentation.

Information relative to premature discontinuation of the study vaccine will be documented in the eCRF. The Investigator will document which of the following reasons was responsible for withdrawal:

- SAE
- AE (non-SAE)
- Dosing error
- Other (specify)

Participants who withdraw from further vaccinations after either the first or second vaccination but do not withdraw consent will be followed for safety as noted above, and will provide blood samples for immunogenicity at specified timepoints after their last vaccination (refer to [Table 6](#) and [Table 7](#) in [Appendix 2](#)).

Participants who miss the second vaccination for any reason will still be able to receive the third vaccination, at the discretion of the Investigator. These participants will have safety calls every 28 ± 7 days until Visit 9 (Month 6), and complete all study procedures from Visit 9 through End of Study as outlined in [Table 1](#).

### **7.2. Participant Discontinuation/Withdrawal from the Study**

Participants who are withdrawn will not be replaced.

From an analysis perspective, a “withdrawal” from the study refers to a situation wherein a participant does not return for the final visit foreseen in the protocol.

All data collected until the date of withdrawal or last contact of the participant will be used for the analysis, including collected specimens.

A participant is considered a “withdrawal” from the study when no study procedure has occurred, no follow-up has been performed, and no further information has been collected for that participant from the date of withdrawal or last contact.

Information relative to the withdrawal will be documented in the eCRF. The Investigator will document whether the decision to withdraw a participant from the study was made by the participant or by the Investigator, as well as which of the following possible reasons was responsible for withdrawal:

- AE (specify)
- Death
- Lost to follow-up
- Physician decision (specify)
- Pregnancy
- Protocol violation
- Study terminated by Sponsor
- Withdrawal of consent by participant (specify)
- Participant has received another investigational drug or vaccine other than the study vaccine at any point from Visit 1 (Month 0)
- Other (specify)

Participants who are withdrawn from the study because of SAEs/AEs must be clearly distinguished from participants who are withdrawn for other reasons. Investigators will follow-up with participants who are withdrawn from the study as result of an SAE or AE until resolution of the event.

### **7.3. Lost to Follow-up**

A participant will be considered lost to follow-up if he or she repeatedly fails to return for scheduled visits without stating an intention to withdraw consent and is unable to be contacted by the study site. The following actions must be taken if a participant fails to return to the clinic for a required study visit:

- The site must attempt to contact the participant and reschedule the missed visit as soon as possible, counsel the participant on the importance of maintaining the

assigned visit schedule, and ascertain whether or not the participant wishes to and/or should continue in the study.

- Before a participant is deemed lost to follow-up, the Investigator or designee must make every effort to regain contact with the participant (where possible, 3 telephone calls and, if necessary, a certified letter to the participant's last known mailing address or local equivalent methods). These contact attempts (eg, dates of telephone calls and registered letters) should be documented in the participant's study source document.
- Should the participant continue to be unreachable, he/she will be considered to have withdrawn from the study.
- A participant should not be considered lost to follow-up until due diligence has been completed. Date of withdrawal/lost to follow-up should be the date of last contact with the participant where safety status of the participant was assessed (eg, clinic visit, phone call).

## **8. STUDY ASSESSMENTS AND PROCEDURES**

The study Schedule of Assessments can be found in [Table 1](#) in [Section 1.3](#).

Two additional Schedule of Assessments tables to instruct how to complete study procedures if the participant receives only the first 2 doses (Month 0 and Month 2) or the first dose (Month 0) are presented in [Table 6](#) and [Table 7](#), respectively, in [Appendix 2](#).

### **8.1. Screening**

At Visit Day 1, all screening requirements, including reason for screen failure if a participant is not randomized, must be completed. The Enrollment Page in the eCRF must also be completed.

Based on prior approval from the Sponsor, the Screening visit may be performed across 2 separate clinic visits.

### **8.2. Confirm Inclusion and Exclusion Criteria**

All inclusion and exclusion criteria described in [Section 5.2](#) and [Section 5.3](#) must be met before enrollment (Visit Day 1).

### **8.3. Collect Demographic and Baseline Data**

Demographic and baseline data such as age, month and year of birth, sex, race, ethnicity, weight, and height (BMI will be calculated) will be recorded in the participant's eCRF.

### **8.4. Medical History**

The participant medical history will be obtained during the screening period by interviewing the participant or by reviewing the participant's medical records. Any pre-existing conditions or signs and/or symptoms present in a participant prior to the first study vaccination should be recorded in the eCRF.

### **8.5. Physical Examination and Vital Signs**

A full physical examination will be performed during the screening period according to standard medical practice, including assessment of vital signs, height, and weight. Vital sign measurements include the assessment of body temperature, systolic and diastolic blood pressures, heart rate, and respiratory rate. The information collected will be recorded in the eCRF.

On days of dosing, vital signs will be collected prior to dosing and approximately 60 minutes after dosing, prior to discharge of the participant.

Symptom-directed physical examinations will be performed at all other scheduled timepoints. Interim physical examinations will be performed at the discretion of the Investigator.

Treatment of any abnormality observed during physical examination should be performed according to local medical practice outside the study or by referral to an appropriate healthcare provider at the discretion of the Investigator.

